### 8.3. Prior and Concomitant Therapy

Any medication or therapy given in addition to the study medication is defined as concomitant medication/therapy (CM) and is to be thoroughly documented in the eCRF together with any previous medication administered within 4 weeks prior to the date of the informed consent signature until end of study. These may be prescribed by a physician or obtained by the subject over the counter. Concomitant medication is not provided by Sponsor.

At each study visit, subjects will be asked whether they have taken any medication other than the study medication (used from signing of informed consent through the end of the study), and all medication including vitamin supplements, over-the-counter medications, and oral herbal preparations, must be recorded in the eCRF.

To the extent possible, the dose of any CM required for chronic diseases should be kept as constant as possible throughout the study. Any changes in administration of any CM must be recorded by the investigator in the relevant eCRF page.

Subjects must be instructed to consult first with the investigator prior to take any other medication, including over-the-counter products. The investigator contact the medical monitor for questions regarding episodic use.

### 8.4. Efficacy and Safety Assessments / Variables

The schedule of assessments is described in the [Appendix 18.1](#).

Subject recruitment for the study is competitive through all sites. Subject data must be entered – after written informed consent is obtained– into the eCRF system as soon as possible, including demographic data. Data/results from screening should be added upon availability.

Subjects not entered in the eCRF are not considered as enrolled in the study.

Study visits are categorized according to the following schedule: pre-treatment screening visit (V1), treatment Day 1 (V2), treatment week 4 (V3), treatment week 16 (V4), treatment week 28 (V5), and optionally up to a maximum 12 months of P2Y12 inhibitor treatment after ACS underwent PCI (V6) based on investigator's discretion. The activities planned for all study visits are described in this section.

## 8.4.1 Description of study procedures

### 8.4.1.1 Informed Consent

Subject Informed Consent should be obtained prior to the subject entering into the study and before any study specific assessment and/or procedures are performed (see [Section 12.3](#)).

A unique subject identification number (subject number) will be assigned to each subject at the time of screening; this subject number will be used throughout the study.

### 8.4.1.2 Demographics

Demographic information will be collected at screening, including age, gender and race.

### 8.4.1.3 Medical history and previous medication

Medical history, including LD treatment during the PCI (clopidogrel LD 300 mg or 600 mg; or ticagrelor LD 180 mg), previous clopidogrel MD 75 mg once daily and/or ticagrelor MD 90 mg bid and aspirin 81-100 mg per day and stent type (BMS and/or DES), will be checked and recorded during the screening. Medical history to be obtained will include determining whether the subject has any significant conditions or diseases that stopped at or prior to Screening (time of informed consent). Ongoing conditions are considered concurrent medical conditions.

All relevant previous medication, including all ongoing medication and medication of the last 4 weeks before screening, should be recorded in the eCRF too.

### 8.4.1.4 Physical examination

Complete physical examination will be performed at all study visits. Physical examinations will consist of the following body systems: (1) general appearance; (2) extremities; (3) skin; (4) head and neck; (5) eyes, ears, nose and throat; (6) lungs and chest; (7) heart/ cardiovascular; (8) neurological; (9) abdomen / gastrointestinal; (10) liver; (11) musculoskeletal; and (12) other. Each system should be assessed as normal or abnormal and in this last case if that is clinically relevant or not.

### 8.4.1.5 Vital signs

Vital signs (height [only once at screening], weight, BMI, heart rate and blood pressure) will be assessed at all study visits.

### 8.4.1.6 Pregnancy test

Blood pregnancy sampling will be obtained at screening, at visit 5 (week 28), and optionally at visit 6 (maximum 12 months of P2Y12 inhibitor treatment after ACS underwent PCI) or early termination.

If any subject is found to be pregnant during the study she should be withdrawn and any sponsor-supplied drug should be immediately discontinued and returned to the study site. In addition, any

pregnancies in the partner of a male subject during the study or for 4 weeks after the last dose, should also be recorded following authorization from the subject's partner.

If the pregnancy occurs during administration of active study medication or within 4 weeks of the last dose of active study medication, the pregnancy should be reported immediately, using a pregnancy notification form.

If the female subject, or female partner of a male subject, agrees to the primary care physician being informed, the investigator should notify the primary care physician that the subject was participating in a clinical study at the time the subject/female partner of the subject became pregnant and provide details of treatment the subject received.

All pregnancies from subjects on active study drug will be followed up to final outcome, using the pregnancy form ("EXPOSURE IN UTERO REPORTING FORM"). The outcome, including any premature termination, must be reported to the sponsor. An evaluation after the birth of the child will also be conducted. If the outcome of the pregnancy meets the criteria for immediate classification as a SAE (ie, post-partum complications, spontaneous or induced abortion, stillbirth, neonatal death, or congenital anomaly, including that in an aborted fetus), the investigator should follow the procedures for reporting SAEs outlined in [Section 9.7](#).

#### 8.4.1.7 Procedure for Clinical Laboratory Samples

Blood sampling for local assessment will be obtained at screening (visit 1), Day 1 (visit 2), week 4 (visit 3), week 16 (visit 4), week 28 (visit 5), optionally based on investigator's discretion at maximum 12 months of P2Y12 inhibitor treatment after ACS underwent PCI (visit 6) or early termination. All samples will be collected in accordance with acceptable laboratory procedures. Details of these procedures and required safety monitoring will be provided by the site and archived in the trial master file (TMF). There is no need for fasting conditions for the analyses; but the same fasting or fed conditions should remain the same for all the blood samples obtained and analyzed at the same site for all their corresponding patients. Blood samples obtained from day 1 to week 28 and optionally up to a maximum 12 months of P2Y12 inhibitor treatment after ACS underwent PCI will be taken before prasugrel MD + aspirin administration of each corresponding visit.

All laboratory values outside the normal range must be evaluated and assessed by the investigator for clinical relevance and in this case, they should be recorded in the eCRF as adverse events.

The clinical analyses will be performed in a local laboratory (including hematology, biochemistry and pregnancy testing). An extra blood sample will be obtained at visit 3 (week 4) once during the whole study for the pharmacogenomic central laboratory examination for patients who sign the pharmacogenomic informed consent form separately.

The following parameters will be assessed:

- Platelet function: P2Y12 reaction unit (PRU, also to derive the platelet reactivity [HTPR]), platelet inhibition (%). (See [Section 8.4.1.9](#))
- Hematology: White Blood Cells (WBC), neutrophils, lymphocytes, monocytes, eosinophils, basophils, Red Blood Cells (RBC), Hemoglobin, Hematocrit, Platelet Count.

- Biochemistry: Total protein, albumin, alanine aminotransferase (ALT), aspartate aminotransferase (AST), alkaline phosphatase, total bilirubin, blood urea nitrogen (BUN), creatinine, sodium, potassium, chloride, LDL cholesterol. The estimated glomerular filtration rate (eGFR) will be calculated following the CKD-EPI Creatinine Equation (2009).

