#### 6.2.1.2 Secondary Endpoint(s)

Efficacy (antiplatelet effect):

- Percentage of High on-Treatment Platelet Reactivity (HTPR) defined as PRU > 235.
- Percentage of platelet inhibition at the end of the 4-week MD treatment period, after switching from clopidogrel MD to prasugrel MD.

Safety: Incidence of:

- Major bleeding events (non-coronary artery bypass grafting [CABG] thrombolysis in myocardial infarction (TIMI) major) after 4 MD treatment weeks.
- Minor and clinically relevant bleeding events after 4 MD treatment weeks
- Major adverse cardiovascular events (MACE) including cardiovascular death, non-fatal myocardial infarction (MI), non-fatal stroke, stent thrombosis and revascularization after 4 MD treatment weeks
- All cause deaths after 4 MD treatment weeks
- Adverse events after 4 MD treatment weeks

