**Treatment week 4 (Visit 3, Day 28 ± 14). End of Period 1**

This visit will be performed 4 weeks after the 1st prasugrel MD administration, as the end of the Period 1. The following examinations/procedures will be performed:

- Physical examination
- Vital signs (including blood pressure)
- Laboratory (hematology, biochemistry)
- Laboratory (platelet function) to be done immediately before the daily dose of prasugrel MD + aspirin administration of Visit 3
- Blood sample for CYP2C19 genotyping (before prasugrel MD + aspirin administration of Visit 3)
- Electrocardiogram
- Recording of bleeding events
- Recording of major adverse cardiovascular events
- Recording of all cause death
- Study drug dispensing (prasugrel 3.75 mg)
- Recording of adverse events
- Recording of concomitant medication

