**Early Termination**

In case of an early termination after 1st prasugrel MD administration and before treatment at visit 5 (week 28), the same procedures planned for the treatment at visit 5 (week 28) should be performed.

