### **8.4.4 Exploratory Variables**

The association CYP2C19 genotyping for available subjects (targeted 100 subjects) who have signed the pharmacogenomic informed consent form separately will be assessed as exploratory analysis.

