### 8.5.2 Discontinuation or Withdrawal of Individual Subjects

If a subject having received the 1st prasugrel MD treatment terminates the study prematurely for any reason, all attempts should be made by the investigator to perform the procedures for the early termination visit (same as for the week 28 visit) and determine the primary reason for the termination and where possible the primary underlining reason, providing as much as detail as possible, and documenting the information on the eCRF. .

For subject who terminated before Visit 3, Platelet function tests have to be conducted during the early termination visit.

The primary reason for discontinuation or withdrawal of the subject from the study should be noted using the following categories:

- (1) Adverse Event (AE). The subject has experienced an adverse event that requires early termination because continued participation imposes an unacceptable risk to the subject's health or the subject is unwilling to continue because of the adverse event or pre-treatment adverse event.
- (2) Noncompliance with investigational medicinal product (IMP) prasugrel MD + aspirin.  
Period 1 compliance is defined as 80% compliance in the first 4 weeks with maximum 2 consecutive missed doses in the last week.  
Period 2 compliance is defined as 80% compliance in the 24 weeks (up to 12 months, alternatively)
- (3) Major protocol deviation. The subject failed to meet protocol entry criteria or did not adhere to protocol requirements, and continued participation poses an unacceptable risk to the subject's health, or a major protocol deviation occurred at the site.
- (4) Withdrawal of consent. The subject (or subject's legally acceptable representative) wishes to withdraw from the study. The reason for withdrawal, if provided, should be recorded in the case report form (eCRF). Subjects may withdraw from the study at any time at their own request without giving reasons and without any disadvantageous consequences for their subsequent medical care.
- (5) Lost to follow-up. The subject did not return to the clinic and attempts to contact the subject were unsuccessful. Attempts to contact the subject must be documented.

(6) Other.

In the case of study termination by the sponsor, institutional review board (IRB), independent ethics committee (IEC), or regulatory agency, reason for withdrawal should be captured as Other, Study Termination.

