## 11.1.5 Exploratory Analyses

Association of primary and secondary variables with CYP2C19 genotype will be evaluated. Similar analysis to the described above may be obtained per genotype subgroups when appropriate for the size of the subgroup.

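### CYP2C19 blood is drawn only at Visit 3, so subjects who die or stop before then are never genotyped and the exploratory genotype analyses condition on reaching that visit

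*Combined protocol and SAP*

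**What the plan says.** The protocol gives one time point for the pharmacogenomic sample. Section 8.4.1.7: "An extra blood sample will be obtained at visit 3 (week 4) once during the whole study for the pharmacogenomic central laboratory examination". The Visit 3 procedure list in section 8.4.2 repeats it: "Blood sample for CYP2C19 genotyping (before prasugrel MD + aspirin administration of Visit 3". The schedule in Appendix 18.1 marks the sample under V3 and nowhere else. The visit is headed "Treatment week 4 (Visit 3, Day 28 ± 14). End of Period 1", so it may take place anywhere from Day 14 to Day 42.

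For early termination before Week 28, section 8.4.2 says "the same procedures planned for the treatment at visit 5 (week 28) should be performed". The Visit 5 list contains no genotype sample. Section 8.5.2 adds one item for those who stop early: "For subject who terminated before Visit 3, Platelet function tests have to be conducted during the early termination visit". Footnote (9) of Appendix 18.1 says the same. Neither adds the genotype sample.

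On the analysis, section 11.1.5 states: "Association of primary and secondary variables with CYP2C19 genotype will be evaluated". Those variables include bleeding, MACE and adverse events at 4 and 28 weeks, and, among the Period 1 secondary endpoints in section 6.2.1.2, "All cause deaths after 4 MD treatment weeks". Section 6.1 frames safety as assessed from baseline, and section 11.1 takes everyone with at least one dose as the main population. The genotype subset is a target of 100 subjects with separate consent.

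**The concern.** Genotype does not change over time, so nothing in the measurement itself requires waiting until Week 4, and the documents give no reason for doing so. Waiting makes entry to the genotyped set depend on what happens after the first dose: a subject must survive and stay in the study until Visit 3. Outcomes are nevertheless counted from Day 1.

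Three things follow:

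- The interval from Day 1 to sampling is free of deaths by selection in every genotype group.
- Non-fatal bleeding or MACE that ended participation before Visit 3 is absent from the genotype tables.
- An early terminator tested under section 8.5.2 can have a post-switch PRU but no genotype, so the loss also touches the genotype analysis of the primary PRU variable.

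If early stopping differs by genotype, the missing subjects are the informative ones, and a Kaplan-Meier curve by genotype started at baseline would carry that selection. Section 11 describes no landmark or delayed-entry handling.

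**Working it through.** **1. Tracing the sample.** Visit 1 and Visit 2 lists: no genotype sample. Visit 3: yes. Visits 4, 5 and 6: no. Early termination: Visit 5 procedures, plus platelet function tests if before Visit 3, and no genotype sample. The only route to a genotype is to attend Visit 3.

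**2. The plan's own figures (section 11.2).** 170 completers at 15% drop-out: 170 / 0.85 = 200, as stated. Probability of at least one event at incidence 0.01 in 170 subjects: 1 − 0.99^170 = 0.819, matching the stated 82%. The point does not depend on this second figure. The plan gives no figure for the genotype analysis.

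**3. Subjects lost before sampling.** The documents do not give drop-out timing, so an even spread over 196 days is assumed.

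| Visit 3 on | Fraction of 196 days | Of 30 drop-outs in 200 | Of 15 drop-outs in 100 |
|---|---|---|---|
| Day 14 | 7.1% | 2.1 | 1.1 |
| Day 28 | 14.3% | 4.3 | 2.1 |
| Day 42 | 21.4% | 6.4 | 3.2 |

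A constant hazard instead of an even spread gives 200 × (1 − 0.85^(4/28)) = 4.6 by Day 28 (2.3 to 6.8 across the window), or half of that per 100. With timing left entirely free, the bound is 0 to 30 of 200, or 0 to 15 of 100.

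**4. Events before sampling.** At a constant event hazard, the same fractions apply: 14% (7 to 21%) of 28-week events fall before Visit 3. This is a ceiling on the loss under that assumption, because only events that end participation remove the subject. For illustration, if the 0.01 used in section 11.2 were a 28-week incidence, 100 subjects would have 1 expected event, of which 0.14 (0.07 to 0.21) would fall before Visit 3.

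**5. Four-week deaths.** The documents give no 4-week mortality; take 0.1% to 1% as an assumed range.

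- Sample at Day 1 in 100 subjects: 0.1 to 1.0 expected deaths. P(at least one) = 1 − (1 − p)^100 = 9.5% to 63%.
- Sample at Visit 3, with the 4-week period ending at that visit: 0 deaths.
- Sample at Visit 3, with the period ending on Day 28, in the extreme case of everyone sampled on Day 14: the risk over the remaining 14 days is 1 − (1 − p)^0.5, giving 0.05 to 0.50 expected deaths and P(at least one) = 4.9% to 39%.

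The documents do not say which of the two period ends applies.

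**The case against.** The strongest reply is that little is at stake. The analysis is exploratory and carries no power claim. Section 11.1.5 makes the genotype subgroup analyses optional and dependent on subgroup size. With about 100 subjects, no association with 4-week death could be estimated under either schedule. For the primary PRU variable, nearly every subject with a post-switch value is at Visit 3 and can be sampled there. All of this stands, and it sets the low weight of the point.

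A reader might also infer more than the documents support:

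- **That anyone who bleeds before Visit 3 goes ungenotyped.** Section 8.4.1.10 has bleeding assessed at every visit after the first dose, and section 9.4 allows an adverse event to leave dosing unchanged or only interrupted. A patient who bleeds and continues is sampled.
- **That 4-week deaths in the genotyped set are zero by construction.** That holds only if the period ends at each subject's Visit 3. With a Day 28 cut-off, someone sampled on Days 14 to 27 could still die within the period.
- **That 14% of events are lost.** That fraction counts all events before Visit 3, including those in patients who stay and are sampled.
- **That non-fatal event rates by genotype are necessarily too low.** This requires such events to cause early exit. The documents give no basis for sizing it, or for sizing any distortion of the association.

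None of this supplies a second sampling opportunity or removes the conditioning on reaching Visit 3.

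**Conclusion.** The point holds in a limited form. Subjects who die or discontinue before Visit 3 are never genotyped, including early terminators who do have a post-switch PRU. The genotype associations with outcomes counted from baseline therefore condition on surviving and staying to Visit 3. The genotyped set has no deaths before its sampling date, and few if any by Day 28. It also lacks bleeding or MACE that ended participation before sampling.

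The likely size is about 2 (1 to 3) of 100 targeted subjects, equivalent to 4 (2 to 6) of all 200 enrolled. This rests on the 15% drop-out being spread evenly; more early drop-out would raise it. The event ceiling of 14% (7 to 21%) likewise rests on a constant hazard. Neither period's primary analysis is affected, since only the exploratory genotype breakdown uses this sample. It is worth correcting because the correction is cheap.

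**What to change.** - In sections 8.4.1.7 and 8.4.2 and Appendix 18.1, move the genotyping sample to Visit 2 (Day 1, pre-dose). Draw it at the same venipuncture as the platelet function, hematology and biochemistry blood already planned, with an extra tube for the central laboratory as now.
- Keep Visit 3, or the early termination visit, as a fallback for subjects who give the pharmacogenomic consent later. A sample at early termination mainly serves the PRU association, since such a subject has little follow-up after it.
- In section 11.1.5, base the main genotype-by-event analysis on subjects sampled at Day 1. Include those sampled later only from their sampling date (delayed entry), or in a sensitivity analysis.

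**Cost:** wording in the protocol, schedule and laboratory instructions. The number of genotype samples per subject is unchanged. The separate consent must be offered by Day 1, and a few samples will come from subjects who never provide a Week 4 PRU. For subjects already past Day 1, adding the sample to the early termination visit and stating the conditioning on Visit 3 in the report would recover part of the loss, though not deaths before Visit 3.

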#### **8.4.1.8 Electrocardiogram, heart rate, blood pressure**

A 12-lead ECG will be performed locally at screening (visit 1), treatment week 4 (visit 3), treatment week 28 (visit 5), optionally based on investigator's discretion at maximum 12 months of P2Y12 inhibitor treatment after ACS underwent PCI (visit 6) or early termination. Additional ECGs may be performed at the discretion of the investigator during any follow-up. The findings and any abnormality will be recorded in the eCRF as either medical history (findings at screening) or adverse events (any further finding or change from screening). Standard ECG parameters will be recorded in the eCRF (heart rate, RR, QT, QTc following both Bazzett's and Fridericia's methods).

#### **8.4.1.9 Platelet function**

P2Y12 reaction unit (PRU) with the VerifyNow®, High on-treatment Platelet Reactivity (HTPR), and percentage of platelet inhibition will be assessed at Day 1 (pre-dosing) and treatment week 4 (visit 3). The PRU will be assessed immediately before dosing as that will assess the steady state which is the most appropriate approach for a maintenance dose. For clopidogrel assessment, Day 1 (before prasugrel switch dosing) is selected as being the last day of clopidogrel 75 MD after maximum 4 weeks screening (suggested test timing for clopidogrel 75 mg  $\geq$  6 days of maintenance). For prasugrel assessment, Week 4 is selected as being the last day of prasugrel 3.75 mg MD after 4 weeks treatment Period 1 (suggested test timing for prasugrel 5 mg  $\geq$  5 days on maintenance).

#### **8.4.1.10 Bleeding Events**

Major, minor and clinically relevant bleeding events will be assessed at all study visits after the first prasugrel MD treatment.

#### **8.4.1.11 All cause deaths**

All cause deaths will be assessed at all study visits after the first prasugrel MD treatment.

## 8.4.2 Study Procedures

### Screening assessments (Visit 1, Day -28 to Day -1)

Subjects will be screened for enrolment within 4 weeks prior to the start of prasugrel MD. Subjects will be screened in accordance with predefined entrance criteria as described in [Sections 8.1 and 8.2](#). See [Section 8.5.1](#) for the procedure for documenting screen failures.

Procedures to be completed at screening include:

- Subject information/Informed consent signed and dated.
- Demographics
- Assessment of inclusion / exclusion criteria.
- Medical history and previous medication
- Physical examination
- Vital signs (including blood pressure)
- Laboratory (hematology, biochemistry), serum pregnancy test (for women of childbearing potential)
- Electrocardiogram
- Determination of subject eligibility
- Recording of adverse events

